## 9.4 SUBJECT DISPOSITION

---

The disposition of subjects includes the number and percentage of subjects for the following categories: subjects enrolled, subjects treated (safety population), subjects in the ITT population, subjects completed, and subjects discontinued from the study. The reasons for study discontinuation will also be summarized in this table. Only one primary reason for study discontinuation will be reported in the summary. However, all reasons will be presented in the listing. The disposition will be summarized by treatment group and overall.

A listing will present data concerning subject disposition.

## 9.5 SUBJECT DEMOGRAPHICS AND BASELINE CHARACTERISTICS

---

Baseline demographic and clinical characteristics will be summarized as percentages for categorical variables and as mean, standard deviation, median, minimum and maximum for continuous measures. The analyses of baseline characteristics will be performed for the ITT Population by treatment group and overall.

## 9.6 MEDICAL HISTORY

---

Medical history will be captured at the Screening visit. Medical history will be coded using MedDRA and will be summarized by MedDRA system organ class and preferred term for the Safety population.

## 9.7 EXTENT OF EXPOSURE

---

The dose (mg) of study drugs administered, the total number of doses of study drugs, and the duration of treatment (number of study cycles) will be summarized with descriptive statistics. The number and percentage of subjects whose dose is modified at any time will be summarized by each type of modification by cycle and overall. The proportion of subjects completing each cycle of treatment will be summarized.

## 9.8 EFFICACY ANALYSES

---

All subjects included in the study must have a baseline tumor assessment within 30 days of Cycle 1/Day 1 and at least one post-treatment efficacy evaluation in order to be included in the efficacy analyses. Each subject will be assigned one of the following categories: 1) complete response, 2) partial response, 3) stable disease, 4) progressive disease, 5) early death from malignant disease, 6) early death from toxicity, 7) early death because of other cause, or 9) unknown (not assessable, insufficient data).

---

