 Unilateral bone marrow aspirate and/or biopsy performed at investigator discretion in subjects for whom assessment of extent of CLL involvement and bone marrow cellularity is important. In addition, a post-baseline bone marrow biopsy should be completed to confirm potential CR by radiological assessment.

 For women of child bearing potential, completed within 3 days of Cycle 1 Day 1.

 For women of child bearing potential, completed within 3 days of visit

 Must be obtained prior to ublituximab administration if on day of infusion.

 Must be done within 14 days of cycle 1 day 1

 For del(13q), del(11q), del(17p), and (12) trisomy, t(11:14)

 Scans should be completed approximately 45 days prior to Day 1 of Cycle 1. Radiology assessment should include CT or MRI imaging of chest, abdomen, and pelvis.

 Serum virology to include HBsAg, HbC antibody, HCV antibody and CMV IgG and IgM. If HbC antibody, HCV antibody or CMV IgM is positive, subjects must be evaluated for the presence of active HBV, HCV or CMV by PCR

 Q3 months CMV screening by PCR for all subjects.

 Peripheral blood sample may be analyzed by local lab. For subjects MRD negative by peripheral blood, a bone marrow should be completed to confirm MRD negativity. If a bone marrow is not completed, another peripheral blood sample should be collected to confirm the MRD negativity at least 12 weeks later. MRD should continue to be evaluated for subjects with PR/CR at response assessment intervals until 2 consecutive peripheral blood MRD negative results, or 1 negative peripheral blood MRD and 1 negative bone marrow MRD are observed.

 Subjects who received ublituximab on UNITY-CLL trial (Arm C), will not receive split dosing on Day 1 and 2 of cycle 1. Subjects should receive full dose on Cycle 1, Day 1 and will not receive Day 8, and 15 during Cycle 1.

 If clinically significant adverse event or abnormal result is observed that is not resolved by the end-of treatment visit, continue to monitor and record up through 30 days after study drug discontinuation.

TABLE 2: FOLLOW UP ASSESSMENTS SCHEDULE

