## 5.1 LABORATORY EVALUATIONS - OVERVIEW

All subjects should visit the study center on the days specified within this protocol. The complete schedule of assessments is shown in [Section 5](#). The baseline physical examination with vital signs, medical history, Rai staging, evaluation of concomitant medications, ECOG PS, bone marrow aspirate/biopsy (if applicable), complete blood count/full blood count (3-part differential accepted), serum chemistry, and CLL FISH panel, should be done within 28 days prior to initiation of treatment (14 days for CBC and Chemistry). For women of child bearing potential, a serum pregnancy test should be completed within 3 days (72 hours) prior to Day 1 of Cycle 1 and a urine pregnancy test within 3 days of assessment as per the [table in Section 5](#). Tumor assessment scans should be performed  $\leq 45$  days prior to initiation of treatment. In the event that the subject's condition is deteriorating, laboratory evaluations should be repeated within 48 hours prior to initiation of the next cycle of therapy.

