## 8 MEASUREMENT OF EFFECT

---

During the study period, all subjects will be evaluated for response by CT and/or MRI. Evaluations are to be obtained at approximately cycles 3, 6 and 12. Following cycle 12, evaluations should occur at least every 12 cycles unless clinically indicated more frequently. The determination of response and progression will be based on IWCLL criteria (Hallek M, 2008) by the treating investigator.

CT scan is the preferred method of tumor assessment, but MRI may be used at the investigator's discretion. The same method of assessment and the same technique should be used to characterize each identified and reported lesion at baseline and throughout the study. All baseline assessments to characterize disease will be performed within approximately 45 days of Cycle 1 Day 1, prior to initiation of therapy.

Subjects should remain on study treatment until the occurrence of definitive disease progression, unacceptable toxicity, or withdrawal from the study due to investigator decision or other reasons. Subjects who discontinue from study treatment (either for toxicity or physician choice) and have not progressed will continue to be followed for progression as per the protocol.

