### 9.3 ANALYSIS POPULATIONS

---

The Intent-to-Treat (ITT) population will consist of all subjects who were enrolled and have at least one post-treatment efficacy measurement. Primary efficacy analyses will be performed based on the ITT population.

The Safety Population will include all subjects who were enrolled and received at least one dose of study drug. All safety assessments including toxicity will be performed on the Safety Population.

The Per-Protocol Population (PP) will consist of all ITT subjects without a major protocol deviation. The criteria for a major protocol deviation will be determined and documented prior to data base lock. Subject exclusion from the PP population will also be determined and documented prior to database lock. Supportive analyses may be performed based on the PP population.

Furthermore, in the analyses/summaries, subjects will be assigned a treatment group based on the treatment they received on study UTX-TGR-304 prior to their entering of this Companion Study as appropriate.

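### Section 9.8 requires a baseline scan within 30 days for the efficacy analyses, but the schedule allows about 45 days and the Section 9.3 ITT set has no scan window

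*Combined protocol and SAP*

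**What the plan says.** Two places define who enters the efficacy analyses.

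- Section 9.3: "The Intent-to-Treat (ITT) population will consist of all subjects who were enrolled and have at least one post-treatment efficacy measurement". It adds: "Primary efficacy analyses will be performed based on the ITT population". It sets no condition on a baseline scan.
- Section 9.8: "All subjects included in the study must have a baseline tumor assessment within 30 days of Cycle 1/Day 1". The same sentence also asks for an efficacy assessment after treatment, and a subject must meet both conditions to count in the efficacy analyses.

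Three places define when the baseline scan may be taken.

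- Section 5, Table 1, footnote 11: "Scans should be completed approximately 45 days prior to Day 1 of Cycle 1".
- Section 5.1: no more than 45 days before treatment starts.
- Section 8: "All baseline assessments to characterize disease will be performed within approximately 45 days of Cycle 1 Day 1".

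All of this is current text, not the amendment history. Section 9.3 defines three populations only: ITT, Safety and Per-Protocol. There is no separate response-evaluable set to which a 30-day rule could belong.

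**The concern.** The 30-day rule in Section 9.8 is stricter than the window that sites are told to use, and it is absent from the population that Section 9.3 names for the primary efficacy analyses. Subjects who did everything the schedule asked could lose their place in the analysis, along with their responses.

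The ORR and its 90% one-sided confidence interval (Section 9.8.1) depend on which section the programmer follows. So do the sets for PFS, duration of response and MRD negativity (Section 9.8.2). Two analysts working faithfully from the same plan could report different primary results. The study is open-label and response is judged by the treating investigator (Section 8), so a choice left until the data have been seen would be a post hoc choice of denominator.

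**Working it through.** The plan gives no figure to reproduce: there is no power calculation, and no scan-date distribution is stated. The check is a comparison of the rules followed by simple arithmetic.

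**Step 1: the rules side by side.** Take a treated subject with at least one post-treatment efficacy assessment.

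| Baseline scan, days before Cycle 1 Day 1 | Within schedule (Sections 5, 5.1, 8) | In ITT (9.3) | In efficacy analyses (9.8) |
|---|---|---|---|
| 30 or fewer | yes | yes | yes |
| 31 to 45 | yes | yes | no |
| well over 45 | no | yes | no |

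The post-treatment condition is common to Sections 9.3 and 9.8, so the conflict lies only in the baseline scan condition. The middle row is the problem: compliant, in ITT, and excluded.

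**Step 2: could the middle row be occupied?** Table 1 footnote 1 lets tests done for UTX-TGR-304 be re-used to evaluate eligibility. Subjects from Arms B, C and D need progression confirmed by the IRC, and inclusion criterion 1a sets no time limit for starting treatment afterwards. Section 6.1 starts Cycle 1 for Arm C subjects 28 days after their last parent-study ublituximab dose. Each of these can put time between scan and Cycle 1 Day 1. Footnote 11, read literally, even directs scans to about day -45. Pulling the other way, Table 1 lists tumor evaluation in a screening column that runs from day -28 to day 0.

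**Step 3: size.** Let f be the share of subjects otherwise analysable whose scan falls on days -31 to -45. The documents do not give f. It is 0% if all scans fall within 30 days and 100% if all fall in the band. The band is 45 - 30 = 15 days, so if scan dates were spread evenly over 45 days (an assumption), f = 15/45 = 33.3%.

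*Precision.* Section 9.8 leaves n(1 - f) of n subjects. At an unchanged ORR, and using the large-sample approximation, interval width grows by the factor 1/√(1 - f).

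| Assumed f | 1/√(1 - f) | Wider by about |
|---|---|---|
| 5% | 1.026 | 3% |
| 10% | 1.054 | 5% |
| 20% | 1.118 | 12% |
| 33.3% | 1.225 | 22% |
| 50% | 1.414 | 41% |

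*Point estimate.* The ORR under Section 9.3 is (1 - f) × p_kept + f × p_dropped. Under Section 9.8 it is p_kept. The difference is f × (p_dropped - p_kept), which cannot exceed f in absolute value. With an assumed gap of 20 percentage points between dropped and kept subjects:

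- f = 10%: 0.10 × 0.20 = 0.020, or 2.0 points either way.
- f = 33.3%: 0.333 × 0.20 = 0.067, or 6.7 points either way.

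The documents give no basis for saying which sign applies.

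**The case against.** The strongest case on the other side has four parts.

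- **The stakes are low.** Sections 9.1 and 9.2 rule out formal hypothesis testing and powering, and an analyst could report both sets. This stands, and it limits the severity. It does not excuse defining the primary analysis set in two ways.
- **Section 9.8 could be read as the more specific rule**, adding an evaluability condition to the ITT set. This does not hold up. Section 9.3 assigns the primary efficacy analyses to ITT without that condition, neither section refers to the other, and no evaluable set is defined.
- **The illustrative sizes rest on assumed values of f and an assumed gap in ORR.** That is correct. Only the 15-day band and the bound of f come without a distributional assumption, and the screening column may mean that few subjects are affected.
- **Other things also bear on the denominator.** Section 9.2 makes non-missing assessments the default denominator for percentages, so a subject classed as unknown may or may not count. A window tied to Cycle 1 Day 1 also suits Arm A poorly at 30 or 45 days. Those subjects carry on from where UTX-TGR-304 ended, the synopsis makes PFS and duration of response their primary objectives, and Section 9.8.2 times their PFS from parent-trial randomization. Both points stand. They do not remove the conflict, but they favour deleting the window over writing a 45-day window into Section 9.3.

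**Conclusion.** The concern holds. Section 9.8 excludes protocol-compliant subjects whom Section 9.3 includes in the same primary analysis, and the documents do not say which prevails. The conflict covers 15 of the 45 permitted days. The number of subjects affected cannot be derived from the documents. The effect is nil if every scan falls within 30 days, and otherwise the reported ORR can move by up to f in an unknown direction, with a wider interval under Section 9.8. Type I error, power and decision thresholds are untouched. This should be fixed before database lock, with high confidence in the textual finding and none claimed for any particular value of f.

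**What to change.** **Preferred change.**

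- Remove the 30-day baseline scan condition from Section 9.8 and state there that efficacy is analysed on the Section 9.3 population.
- List a baseline scan outside the 45-day window among the protocol deviations considered for the Per-Protocol set, whose criteria Section 9.3 already leaves to be settled before database lock. Such a scan should affect that set only.
- Place a subject without a usable baseline in the existing unknown response category of Section 9.8. Say explicitly whether that category stays in the ORR denominator, since the Section 9.2 default would otherwise leave this open.
- Word the scan window identically in Section 5 (footnote 11), Section 5.1 and Section 8, as either a firm 45-day maximum or an approximate one.

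**Minimum change.** Align Section 9.8 with the 45-day window, worded the same way throughout, and repeat the same condition in Section 9.3. This removes the contradiction but keeps a window that fits Arm A poorly.

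**Cost.** Edits to Section 9.8, a cross-reference to Section 9.3, one line in the deviation criteria, and consistent wording of the window. Data collection does not change. The trade-off is that baseline scans up to about 15 days older than Section 9.8 now accepts serve as the response reference, which the schedule already permits.

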### 9.8.1 PRIMARY EFFICACY VARIABLE

---

Overall response rate (ORR), where  $ORR = \text{complete responses (CR)} + \text{partial response (PR)}$ , will be the primary efficacy variable. The overall response rate (ORR) and the 90% one-sided confidence interval of the rate will be estimated by treatment group, if appropriate (i.e., if sample sizes are sufficient) and overall.

CR and PR will be similarly analyzed as ORR.

---

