Study Objectives	
For subjects previously on Arms B, C, & D of Study UTX-TGR-304:
 
Primary Objectives
 
 
To observe the overall response rate (ORR) defined as the sum of complete responses (CR) and partial responses (PR)
 
 
Secondary Objective
 
 
To observe the progression-free survival (PFS) and duration of response (DOR)
 
To observe the % of subjects that achieve MRD negativity
 

	
 
To observe the safety of ublituximab in combination with TGR-1202
 
 
For subjects previously on Arm A of Study UTX-TGR-304:
 
Primary Objectives
 
 
To evaluate the progression-free survival (PFS) and duration of response (DOR)
 
 
Secondary Objective
 
 
To evaluate the safety of ublituximab in combination with TGR-1202
 

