#### **Primary Objectives**

- To observe the overall response rate (ORR) defined as the sum of complete responses (CR) and partial responses (PR)

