#### **Secondary Objective**

- To observe progression-free survival (PFS) and duration of response (DOR)
- To observe the % of subjects that achieve MRD negativity
- To observe the safety of ublituximab in combination with TGR-1202

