### 3.1 INCLUSION CRITERIA

---

1. Prior treatment in clinical trial [UTX-TGR-304](#)
  - a. Confirmed progression by IRC on Arms B, C, or D after at least two cycles of treatment in trial UTX-TGR-304. There is no required timeframe to begin treatment on the UTX-TGR-204 protocol; however, if other therapies to treat the disease are implemented in the interim, the subject will not be eligible to enroll in the study.
  - b. Non-progressing subjects on Arm A may be eligible for enrollment when protocol UTX-TGR-304 is completed.
2. Adequate organ system function, defined as follows:
  - a. Absolute neutrophil count (ANC)  $> 750 \times 10^3/\text{mm}^3$  (0.75 K/ $\mu\text{L}$ ) / platelet count  $> 40 \times 10^3/\text{mm}^3$  (40 K/ $\mu\text{L}$ ) unless cytopenias are related to bone marrow involvement.
  - b. Total bilirubin  $\leq 1.5$  times the upper limit of normal (ULN) with the exception of Gilbert's Disease and Autoimmune Hemolytic Anemia.
  - c. Alanine aminotransferase (ALT) and aspartate aminotransferase (AST)  $\leq 2.5 \times$  ULN if no liver involvement or  $\leq 5 \times$  the ULN if known liver involvement
  - d. Calculated creatinine clearance  $> 30$  mL/min (as calculated by the modified Cockcroft-Gault formula).
3. ECOG performance status  $\leq 2$
4. Ability to swallow and retain oral medication
5. Willingness and ability to comply with trial and follow-up procedures, give written informed consent

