#### Treatment Schema for Subjects Crossing over from Arm A:

Subjects who crossover from Treatment Arm A will continue their treatment where they left off at the termination of [protocol UTX-TGR-304](#).

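### The synopsis makes ORR primary for Arms B, C and D only, but Sections 2.1 and 9.8.1 drop that limit, specify no B+C+D estimate and do not say how Arm A response is scored

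*Combined protocol and SAP*

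**What the plan says.** **Objectives.** The synopsis splits them by parent arm. For Arms B, C and D, ORR is primary, and PFS, DOR and MRD negativity are secondary efficacy objectives. For Arm A the primary objective is "To evaluate the progression-free survival (PFS) and duration of response (DOR"), and there is no ORR objective. Section 2.1 has one unsplit list: the primary objective is "To observe the overall response rate (ORR) defined as the sum of complete responses (CR) and partial responses (PR"), and the secondary list includes "To observe progression-free survival (PFS) and duration of response (DOR").

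**Analysis.** Section 9.8.1 names ORR as the primary efficacy variable with no arm limit. ORR and a one-sided 90% confidence interval "will be estimated by treatment group, if appropriate (i.e., if sample sizes are sufficient) and overall"; CR and PR are handled the same way. Section 9.8.2 lists PFS and DOR as secondary for everyone, but gives Arm A its own starting points: PFS runs from Study 304 randomization, and DOR from the first documented 304 response unless the best 304 response was stable disease.

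**Who is counted.** Treatment group means the Study 304 arm (Section 9.3). "The Intent-to-Treat (ITT) population will consist of all subjects who were enrolled and have at least one post-treatment efficacy measurement". Section 9.8 adds that subjects "must have a baseline tumor assessment within 30 days of Cycle 1/Day 1 and at least one post-treatment efficacy evaluation" to enter the efficacy analyses.

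**Who Arm A subjects are.** "Non-progressing subjects on Arm A may be eligible for enrollment when protocol UTX-TGR-304 is completed" (Section 3.1). "Subjects who crossover from Treatment Arm A will continue their treatment where they left off" (Section 6.1). Subjects from Arms B, C and D start the combination after progression confirmed by the independent review committee.

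**The concern.** Two statements of the primary objective are both in current text and cannot both govern. An analyst following Section 9.8.1 would report an all-arm ORR as the primary result. The synopsis calls for an ORR in Arms B, C and D, and the plan never commits to producing it as a single estimate with an interval.

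The two populations answer different questions. In Arms B to D, a response is an effect of starting the combination after progression on something else. In Arm A, subjects were selected for not having progressed on that same combination. Mixing them changes what the rate measures.

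The mixture is also not fully defined, because the plan does not say from which baseline Arm A response is scored. Two analysts could both follow the document and report different primary rates. Arm A's own primary endpoints are affected by the same mismatch: PFS and DOR are primary in the synopsis and secondary in Sections 2.1 and 9.8.2.

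**Working it through.** The plan has no figure to reproduce. Sections 9.1 and 9.2 state that there is no powering and no hypothesis test, and the limit of about 700 subjects is the parent study's enrollment.

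**Step 1: which ORR estimates are specified?**
- By 304 arm: conditional on adequate numbers (9.8.1).
- Overall: unconditional (9.8.1), on an ITT set that does not exclude Arm A (9.3).
- B+C+D combined: not specified anywhere. The synopsis statistical text also offers only grouping by prior 304 treatment and overall.

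The entry conditions in 9.8 may remove individual Arm A subjects but do not remove the arm.

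**Step 2: is the Arm A response reference stated?**
- Best overall response runs from the start of treatment (8.3), with no study named.
- Baseline imaging is tied to Cycle 1 Day 1, within about 45 days in Section 8 and 30 days in 9.8. Neither says which Cycle 1 applies to subjects continuing therapy.
- CR (8.4) uses absolute criteria, with no percentage fall from baseline.
- PR (8.5) needs at least two of five criteria, except where only lymphadenopathy, with or without lymphocytosis, is present at baseline. A 50% fall in nodal SPD is one of the five. Some others can be met by reaching a threshold, such as a lymphocyte count below 4 x 10^9/L or a spleen of 12 cm or less, when the abnormality was present at baseline.
- PFS and DOR have explicit 304 starting points for Arm A (9.8.2). Response has none.

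**Step 3: size, as an illustration.** Let s be the Arm A share, pA the Arm A ORR and pB the B+C+D ORR.

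Pooled ORR = s x pA + (1 - s) x pB, so shift = s x (pA - pB).

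Assumed inputs: s from 5% to 40% (the documents give none). pA from 10% (an assumed lower limit under a 204 baseline) to 100% (an upper limit if 304 responses carry over). pB is 45%, or 6/9 = 67%, the CLL/SLL rate in Section 1.5, which comes from a small and different population.

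| Arm A share | pB = 45%: pooled ORR | Shift (points) | pB = 67%: pooled ORR | Shift (points) |
|---|---|---|---|---|
| 5% | 43.3% to 47.8% | -1.8 to +2.8 | 63.8% to 68.3% | -2.8 to +1.7 |
| 10% | 41.5% to 50.5% | -3.5 to +5.5 | 61.0% to 70.0% | -5.7 to +3.3 |
| 20% | 38.0% to 56.0% | -7.0 to +11.0 | 55.3% to 73.3% | -11.3 to +6.7 |
| 40% | 31.0% to 67.0% | -14.0 to +22.0 | 44.0% to 80.0% | -22.7 to +13.3 |

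Example: 0.40 x 1.00 + 0.60 x 0.45 = 0.67, a shift of 0.40 x 0.55 = +22 points. The sign changes where pA = pB.

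**Step 4: a case where by-arm results might be omitted.** Assume N = 50, with 20 from Arm A and 30 from B to D (about 10 per arm). Arm A contributes 2/20 or 20/20 responders. Section 9.8.1 gives neither the interval method nor its direction, so exact (Clopper-Pearson) one-sided 90% lower bounds are used.

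| B+C+D alone | Pooled, Arm A 2/20 | Pooled, Arm A 20/20 |
|---|---|---|
| 14/30 = 46.7%, bound 33.8% | 16/50 = 32.0%, bound 23.2% | 34/50 = 68.0%, bound 58.1% |
| 20/30 = 66.7%, bound 53.4% | 22/50 = 44.0%, bound 34.3% | 40/50 = 80.0%, bound 70.9% |

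**The case against.** The strongest reply is that little is lost. The study is descriptive. Groups are assigned by 304 arm, listings are sorted by arm, and where by-arm results are shown anyone can add B, C and D together. Arm A subjects can enter only once Study 304 is completed, so their share may be small or zero. Section 9.2 even describes access to the combination as the primary objective. All of this stands and limits the consequence. It does not settle which objective is primary, and the addition is possible only if the conditional by-arm results are reported.

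A second reply is that the plan already treats Arm A as a cohort that began in Study 304: PFS and DOR are both dated from there, and treatment continues. DOR is also summarized for responders by treatment group, which implies that 304 responders count as responders. This is a fair inference and makes carry-over the more natural reading. It is still an inference from the DOR rule, because 9.8.1 and Section 8 do not say it for response.

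A reader might also infer that a 204 baseline would turn most Arm A subjects into non-responders and pull the pooled ORR down sharply. The documents do not support that. A subject entering in CR can still meet the absolute CR criteria, and PR does not in general depend on a new 50% nodal fall. A fall in the pooled rate is possible for subjects entering in PR, but the 10% Arm A rate behind the downward figures is only an assumed lower limit.

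**Conclusion.** The inconsistency is real and should be fixed. The synopsis and Sections 2.1, 9.8.1 and 9.8.2 assign different primary endpoints to Arm A. The only guaranteed ORR is an overall one that includes any Arm A subjects who qualify. No B+C+D estimate is specified, and the Arm A response baseline is not stated.

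The effect is on the meaning of the reported primary estimate. A reader might infer a known bias, such as an inflated ORR, or a loss of error control. Neither follows. Carry-over of 304 responses would raise the pooled figure only if Arm A's rate exceeds that of B to D, and there is no test whose error rate could be affected.

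Size depends on assumed inputs throughout. It is under 3 points either way at a 5% Arm A share. At 40% it is -14 to +22 points with a B-D ORR of 45%, or -23 to +13 points with 67%; the lower ends rest on the assumed 10% Arm A rate. With no Arm A subjects it is zero. The problem is greatest if Arm A is a substantial share and the B, C and D groups are too small to report separately.

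**What to change.** Align Sections 2.1, 9.8.1 and 9.8.2 with the synopsis. The documents do not say which version governs, so this is a choice; the synopsis is proposed because it separates the two populations.

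- Restrict the primary ORR, and the CR and PR rates, to Arms B, C and D. Give one combined B+C+D estimate with its one-sided 90% interval, and by-arm results where sizes allow.
- List PFS and DOR as primary for Arm A.
- Report Arm A response separately and descriptively. State in 8.3 and 9.8 whether its reference is the 304 or the 204 baseline, and what Cycle 1/Day 1 means for that arm.
- Label any all-arm ORR as descriptive.

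If the sponsor prefers an all-arm primary ORR, the synopsis should be changed to match and the Arm A response baseline stated.

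The cost is wording in 2.1, 8.3, 9.8, 9.8.1 and 9.8.2, with no new data. The downside is a smaller n for the primary ORR, for example 30 in place of 50 at an assumed 40% Arm A share.
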